PRAGMA-CF	Perth-Rotterdam Annotated Grid Morphometric Analysis for CF					
PBS	Phosphate Buffered Saline					
QALY	Quality-Adjusted Life-Years					
RV	Residual Volume					
GST	Guy's and St Thomas' NHS Foundation Trust					
SHIELD CF	Study of Host Immunity and Early Lung Disease in CF					
TLC	Total Lung Capacity					
WOCBP	Women of Childbearing Potential					

HYPOTHESIS AND SPECIFIC AIMS FOR PARENT STUDY

Hypothesis

- a. Use of ETI in routine clinical practice is associated with significant and sustained improvements in airway, liver and gastrointestinal outcomes and quality of life in children and adults with cystic fibrosis.
- b. Adherence to routine therapies will decrease after initiation of ETI

Specific Aims

- 1. To determine the effect of treatment with ETI on pulmonary function (FEV1 and LCI) in children and adults with CF over a period of 2 years.
- 2. To determine the effect of treatment with ETI on spirometry-controlled CT scores in children and adults with CF over a two-year period.
- 3. To determine the effect of treatment with ETI on airway infection and inflammation in children and adults with CF
- 4. To determine the effect of treatment with ETI on nutrition, gastrointestinal symptoms, gut inflammation and pancreatic function in children and adults with CF over a two-year period
- 5. To determine the effect of treatment with ETI on CF liver disease in children and adults with CF over a two-year period.
- 6. To determine the effect of treatment with ETI on antibiotic treatment of pulmonary disease in children and adults with CF over a two-year period
- 7. To assess the impact of the introduction of ETI on adherence with overall medical treatments for CF

HYPOTHESIS AND SPECIFIC AIMS FOR EXTENSION STUDY

Hypothesis

a. Use of ETI in routine clinical practice is associated with significant and sustained improvements in airway, liver and gastrointestinal outcomes and quality of life in children and adults with cystic fibrosis.

Specific Aims

- 1. To determine the longitudinal effect of ETI on pulmonary function (FEV1 and LCI) in children and adults with CF over an additional period of 5 years.
- 2. To determine the longitudinal effect of ETI on spirometry-controlled CT scores in children and adults with CF over an additional period of 5 years
- 3. To determine the effect of treatment with ETI on airway infection and inflammation in children and adults with CF.

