The design of RECOVER is specifically aimed at maximizing the research benefit (and ultimately the benefit to people with CF) from this cohort of children, adolescents and adults with CF. Our aim with this study is collect as comprehensive as possible an array of biological samples and clinical data from this cohort, and to follow them longitudinally. After the end of RECOVER, we envisage an ongoing surveillance study involving this group, in collaboration with our registry partners so that we can continue to learn about the longer-term impacts of these treatments. In addition, our sample storage plan associated with RECOVER will allow us to work with collaborators and collect, aliquot and store biological samples that will magnify the benefit of the study in light of the fact that these samples will be linked to a well phenotyped cohort with a wide array of useful clinical outcome measures.

EXPERIMENTAL DESIGN AND METHODS

Study Design

RECOVER is a multi-centre, cohort study which takes part in seven paediatric and adult sites across Ireland and the UK over a two-year period (parent study) and a further five years follow up (extension study) in conjunction with the CF Registry of Ireland (CFRI) and the UK CF registry. On the basis that drug will become available first for people aged 12 and over, the first phase, RECOVER12+ will recruit children 12 years and older and adults. This will be followed by the second phase, RECOVER6, recruiting children aged 6-11 years who will likely be starting on drug approximately a year after the older cohort. Data collection for each of these phases will occur over a two year period (Parent Study), and will overlap by 1-2 years. Subsequent to the twoyear period, participants will enter an extension study for a period of five years, with a scaled back programme of assessments occurring annually or biennially. For subjects in both these cohorts, the decision to implement Kaftrio treatment is made completely independently of the decision to enter the study. The investigators will

follow the requirements of the local approved Kaftrio SmPC for the patient management as detailed in the 'special warnings and precautions for use' (e.g. management of hepatic impairment, rash, ophthalmological monitoring, between others), and for the management of interaction with other medicinal products and other forms of interactions.

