• What level of adherence with ETI is seen in the real world?

Measures of weekly adherence (using the three measures independently) will be reported and compared to previously published data on adherence rates with Ivacaftor(115, 147). Adherence over time, using all three methods, will be reported in a weekly fashion as treatment progresses. Changes in adherence over time (weekly, quarterly) will be assessed per individual and cross sectionally. We will explore the relationship between weight gain and subsequent adherence to ETI (because of concerns on behalf of some PWCF about excessive weight gain on modulators).

• Does adherence with other CF therapies decrease after ETI?

Adherence rates, using MPR and self-reported adherence, to medications individually and in groups (vitamins, mucolytics, nebulized antibiotics etc.) will be collected from 3 months prior to the introduction of ETI. The absolute change in adherence for 4 quarters (one before and three after) will be compared using chi squared and ANOVA. The rate of change of weekly adherence will be compared prior to and in the 9 months after (in 3 quarters) initiation of ETI using ANCOVA.

• Does poor adherence adversely affect outcomes?

This question will be addressed from the point of view of firstly, adherence with ETI, and secondly, adherence with other groups of medications. Medium term effects will be determined by comparing overall 12 and 24-month MPRs for given medications and groups of medications and specific relevant outcome measures such as CT scores, LCI, FEV1, nutritional status, antibiotic use and exacerbations at the end of 12 and 24 months respectively.

• Is adherence related to treatment burden?

Results from the various adherence measures will be compared, within individuals, to the CFQ-R treatment burden subscale results at each timepoint.

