Eligibility Assessment	Х	Х															
Sweat Chloride		Х				Х		Х				Х	Х	х	Х	х	Х
LCI	Х	Х				Х		Х		Х		Х	Х	Х	Х	Х	Х
Spirometry-controlled CT (A*)		Х						Х				Х		X1		X1	
Height/Weight/BMI*	Х	Х			Х	Х	Х	Х	Х	Х	Х	Х	Х	Х	Х	Х	Х
FEV1*	Х	Х			х	Х	Х	х	Х	Х	Х	Х	Х	х	х	Х	Х
Airway Sampling (Micro)*	Х	Х			Х	Х	Х	Х	Х	Х	Х	Х	Х	Х	Х	Х	Х
Nasal Lavage (A*)		Х				Х		Х				Х	Х	х	х	Х	Х
FeNO	Х	Х				Х		Х									
Liver Function Testing*		Х			Х	Х	Х	Х				Х	Х	х	Х	Х	Х
Liver Ultrasound		Х						Х				Х	Х	Х	Х	Х	Х
Sputum Collection (A*)		Х				Х		Х		Х		Х	Х	х	Х	Х	Х
Liver Examination		Х						Х				Х					
Stool Collection		Х	Х			Х						Х	Х	х	Х	Х	Х
Blood Collection		Х						Х				Х	Х	Х	Х	Х	Х
Breath Sample Collection		Х			Х	Х	Х	Х									
Abdominal Symptom Score	Х	Х	Х	Х		Х		Х				Х	Х	х	Х	Х	Х
CFQ-R		Х				Х		Х				Х	Х	Х	Х	Х	Х
Pharmacy Records MPR								Х				Х					
Adherence Questionnaire	Х	Х			Х	Х	Х	Х	Х	Х	Х	Х					
MEMs Caps Reading (M)								Х				Х					
Antibiotic Use		Х						Х				Х					
Adverse Event Check			Х	Х	Х	Х	Х	Х	Х	Х	Х	Х	Х	Х	Х	Х	Х
Mental Health Questionnaire													Х	Х	Х	Х	Х

* Collected as normal clinical care,

A - Advanced arm testing in RECOVER parent study

¹ Only for patients who performed spirometry-controlled CT in parent study. Scan at years four and six at sites doing routine clinical CT. Scan at year six for sites not performing biennial CT

M - MEMs study only

Table 14. Schedule of assessments. Each visit has a study window. For the RECOVER parent study the baseline visit (0 month visit) will have an 8 week pre commencement on ETI start window. The 1, 2 and 3 month visits have +/- 2 week window. The 6, 9, 12, 15, 18, 21 and 24 month visits have +/- 1 month window. For the RECOVER extension study each annual visit will have a window of +/- 4 month.

Study Governance and Management Plan

RECOVER

[figure not shown]

Figure 6 RECOVER study management structure.

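### The tests of hypothesis (b) stop at month 9 although adherence is collected to month 24, so a gradual fall is diluted and a late one largely or wholly unseen

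*Protocol*

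**What the plan says.** Hypothesis (b) of the parent study is "Adherence to routine therapies will decrease after initiation of ETI". Aim 7 is "To assess the impact of the introduction of ETI on adherence with overall medical treatments for CF". Neither gives a time horizon, whereas aims 1, 2, 4, 5 and 6 each name two years.

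The Data Analysis part of Specific Aim 7 (Parent Study) asks whether adherence with other therapies decreases after ETI. MPR and self-report data "will be collected from 3 months prior to the introduction of ETI", and two analyses follow:

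- Level: "The absolute change in adherence for 4 quarters (one before and three after) will be compared using chi squared and ANOVA".
- Slope: the weekly rate of change before ETI is compared with that "in the 9 months after (in 3 quarters) initiation of ETI using ANCOVA".

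Table 14 marks the row "Adherence Questionnaire" at months -3, 0, 3, 6, 9, 12, 15, 18, 21 and 24, and the pharmacy-record MPR at months 12 and 24. The Medication Possession Ratios section has MPR calculated locally for 6-month periods before upload.

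Later adherence data do have stated uses, but for other questions: 12- and 24-month MPR against clinical outcomes, and all adherence measures against treatment burden. The weekly and quarterly changes over time described in the same section concern adherence to ETI itself. The general Statistical Analysis section plans mixed models and trajectory analyses without naming adherence. No effect size, SD or power is given for adherence.

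**The concern.** A two-year study states as one of its two hypotheses that routine treatment will fall away once ETI starts, yet both tests of it close at nine months, and no reason is given. If people drop routine treatments gradually as they feel well, most of the fall would lie after the window. A null result at month 9 could then be reported as no decline, although the study holds 15 further months of data on the question.

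There is a smaller, second issue. A single pre-ETI quarter is set against three quarters from the other parts of the year. If treatment use has an annual cycle and ETI starts cluster in the calendar, part of the before/after difference could be seasonal.

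**Working it through.** **1. The window.** Three quarters × 3 months = 9 months, which agrees with the nine months stated for the slope analysis. Follow-up is 24 months, so 24 − 9 = 15 months (five of eight post-ETI quarters) lie outside. The questionnaire visits outside are months 12, 15, 18, 21 and 24.

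**2. Share of a fall that the window sees.** Assume a linear fall from month 0 to month 24 (the Protocol states no shape). The share reached by a period equals its midpoint divided by 24.

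- Quarters 0-3, 3-6 and 6-9 averaged: 4.5/24 = 18.75%.
- Quarter 6-9 alone: 7.5/24 = 31.25%.
- Months 12-24: 18/24 = 75%.
- Quarter 21-24: 22.5/24 = 93.75%.

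If the fall starts at month 6 and is linear to month 24, quarter 6-9 shows 1.5/18 = 8.3%, and the three-quarter mean is 8.3/3 = 2.8%. If it starts at month 9 or later, both are 0%.

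**3. Power, for illustration.** Assumptions, none from the Protocol: a final linear fall of 10 points, a within-person quarterly SD of 15 or 20 points with independent errors, two-sided 5%, and n = 100 or 200 (the recruitment cap is 254). Power = Φ(d/SE − 1.96).

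- Pooled contrast, pre-quarter against the mean of three: d = 1.875, SE = SD × √(1 + 1/3)/√n.
- Trend contrast over the same four quarters, weights −3, −1, 1, 3: the quarterly falls are 0, 0.625, 1.875 and 3.125, so d = −0.625 + 1.875 + 9.375 = 10.625 and SE = SD × √20/√n.
- Pre-quarter against the mean of the four quarters in months 12-24: d = 7.5, SE = SD × √(1 + 1/4)/√n.

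| Contrast | n=100, SD 15/20 | n=200, SD 15/20 |
|---|---|---|
| Pooled, to month 9 | 19% / 13% | 33% / 21% |
| Trend, to month 9 | 35% / 22% | 61% / 39% |
| Months 12-24 | 99% / 92% | over 99% |

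A second set of assumptions (total SD 25 points, within-person correlation 0.5 to 0.7, n = 254) points the same way. For a 10-point fall, power is 0.31-0.47 for the pooled contrast and 0.51-0.73 for quarter 6-9 alone, against more than 0.99 for quarter 21-24. For a 20-point fall, it is already 0.83-0.97 pooled and at least 0.98 for quarter 6-9.

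**4. Season.** The quarters lying 12 and 24 months after (−3, 0) are 9-12 and 21-24; both are outside the window. For an annual cosine of amplitude A, averaging over a quarter multiplies the amplitude by sin(π/4)/(π/4) = 0.90. The four quarters of a year sum to zero, so the other three average −1/3 of the pre-quarter value. The largest shift is therefore (4/3) × 0.90A = 1.2A. With A assumed at 3 to 5 points, that is 3.6 to 6.0 points, and only if everyone starts ETI at the same time of year. Among questionnaire visits, months −3 and 9 are exactly 12 months apart and both lie inside the window.

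**The case against.** The Protocol does not contradict itself here. Hypothesis (b) and aim 7 set no horizon, and nine months is a possible reading of the impact of introducing ETI. That stands: this is a weak choice of window, not an inconsistency.

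Several stronger readings are tempting, and the document does not support them:

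- *That the later data are discarded.* They serve the outcomes and treatment-burden questions and could enter the general mixed models. What is true is that no stated analysis uses them to test for a decrease in other therapies.
- *That a gradual fall is missed.* An early or large fall is detectable within the window. The planned comparison of slopes is aimed at gradual change, and the trend row above shows that a pooled contrast alone overstates the loss. Near-complete blindness applies only to a fall that begins after about month 6 to 9.
- *That season is fully confounded with before/after.* This would need all starts in one season. The Protocol gives no start dates, spread starts shrink the bias, and self-report already has one matched pair (−3 and 9).
- *That later data are pure gain.* Adherence has no concurrent control, and the Protocol's own background says adherence may have fallen by 50% by transition to adult services. A contrast at month 24 therefore mixes ageing with any ETI effect, which a shorter window limits. This is a good reason to keep the nine-month result and not to make the season-matched contrast the sole main analysis.

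Finally, quarterly MPR is not in the planned upload, so the fix cannot assume it.

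**Conclusion.** The point holds as a cheap and worthwhile improvement. Both stated tests of hypothesis (b) close at month 9 while adherence is collected to month 24, and nothing else in the Protocol tests for a later decrease. Under a linear fall to month 24, the analysed quarters average 19% of the final fall and the last of them shows 31%, against 75% over months 12-24. A fall starting at month 9 or later is unseen.

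The shares depend on the assumed shape. The power figures depend also on the assumed fall and SD, and should be read as direction rather than as estimates for this study. The seasonal bias is at most about 1.2 times the seasonal amplitude, and is smaller or absent if starts are spread over the year.

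**What to change.** In the Data Analysis part of Specific Aim 7, for the question on other CF therapies:

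- Extend the within-person comparison to all post-ETI data to month 24. Use self-report by quarter. Use MPR by the 6-month periods already planned for upload, or by quarter if derived from the dispensing records.
- Keep the nine-month comparison and label it the early result.
- Report the 12- and 24-month season-matched contrasts alongside it.
- Adjust for age, and say that later changes may partly reflect ageing because there is no concurrent control.

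No new visits are needed. For self-report the change is one of wording. For MPR by quarter, sites would have to derive quarterly values from records they already obtain. The final answer to hypothesis (b) waits until month 24.

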It is known that poor adherence to pharmacological treatment and medical advice is a global problem and is particularly important in chronic diseases(110). Historically the core treatment for CF was symptom management often involving complex pharmacological treatments that become extensive with increasing age. When viewed in combination with other required treatments such as physiotherapy, it is perhaps unsurprising that many people with CF report significant time burdens associated with daily treatments (111). Adherence is defined as "the extent to which a person's behavior - taking medication, following a diet and/or executing lifestyle changes - corresponds with agreed recommendations from a healthcare provider". Adherence in CF is suboptimal, and poor adherence has been linked to an increased burden of illness and greater healthcare costs(112, 113). Parents or guardians exhibit greater responsibility of treatment in younger children, whilst in adolescence parental influence reduces. By the time patients are transitioning to adult services, adherence may have reduced by 50%(112). Despite the well-known disease-modifying benefits of the already licensed CFTR modulator lvacaftor, studies have found adherence to be suboptimal (114, 115).

P.I. [name]

Self-reporting is the most widely used method for measuring medication adherence due to ease of implementation and low cost. The limitations of self-reporting are that the patient can often over estimate adherence or fail to disclose non adherence due to recall bias (116).

A second method is medication pick-up rates which can identify patients at risk for treatment failure (117). This information is usually extracted from the computerized system in community pharmacies. A limitation is that it measures maximum possible adherence.

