FEV1 measured by spirometry is the most widely used evaluation of lung function in CF. As FEV1 has been used as the primary endpoint in numerous clinical trials in CF to date, it is important that the rate of FEV1 change is recorded and analyzed as a secondary endpoint in this study. Spirometry will be carried out on each subject at three monthly intervals throughout the duration of the parent study, and annually during the extension study as part of routine clinical care. Spirometry will be performed according to the American Thoracic Society (ATS) guidelines(125). Spirometry values collected as part of routine clinical care will be used for this study, rather than repeating this testing specifically for the purposes of the study. Other spirometric measures such as FVC, FEV1/FVC and FEF25-75 will be collected for inclusion in later analyses. The absolute and relative changes and rate of change in % predicted FEV1 (GLI – Global Lung Initiative) will be assessed from baseline to annual subsequent follow up periods.

Lung Clearance Index

LCI will be performed with the Exhalyzer D multiple breath washout device (Eco Medics AG, Duernten, Switzerland). The test itself is usually completed within twenty to thirty minutes (the test takes longer the more airway disease is present) and will be performed according to the European Respiratory Society / American Thoracic Society consensus statement 2013 on the performance of multiple breath inert gas washout(126).. MBW operators will be trained and certified by the team at Guy's and St Thomas' NHS Foundation Trust) under the supervision of [name]. Centralized over-reading will be completed at the RBH centre. All tests will be performed in replicate, and average values calculated for acceptable trials. LCI will be performed pre-bronchodilator in all subjects. LCI will be performed three months prior to the baseline visit and then at baseline and at 6 monthly intervals subsequently for the parent study, and annually during the extension study..

Analysis plan

The primary endpoint for LCI for the parent study will be the absolute difference in LCI in children on ETI compared the pre-treatment baseline. An interim analysis will be completed after one year of treatment, and a final parent study analysis at the end of two years. Subsequent annual and multi-annual change in LCI will be assessed during the extension study.

Risks with FEV1 and LCI Data Collection

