Statistical analysis of longitudinal data requires methods that can properly account for the intra-subject correlation of response measurement. Preliminary analysis of treatment group means over the time periods will inform more complex analyses of derived variables such as slopes, pre/post analysis and response trajectory over time. Linear mixed models will include demographic and co-morbidity covariates to adjust for confounders. Random effects will account for correlation among repeated measurements. Data transformation and distributional assumptions will depend on the types of data. A Normal distribution will be assumed for continuous variables. A Poisson distribution and log transformation will be assumed for count data. Categorical data will be analyzed using logistic or multinomial regression where appropriate. Model diagnostics will be applied to assess model fit, distributional assumptions and potential outliers. Where distributional assumptions are not met, non-parametric alternatives will be employed. Where there are multiple outcome measures relating to a specific aim, multiple comparison adjustments may be necessary. False discovery rate (FDR) adjustments will be applied where appropriate.

Biosample Collection, Processing and Storage Plan For Parent Study

Blood

Blood (15ml) will be collected, where possible, during clinically indicated venepuncture. And aliquoted as follows:

- 5ml in EDTA tube for DNA extraction. Sample transferred to the lab and frozen at -80°C for later transfer to Central labs and thereafter to our collaborators in Toronto (FR). This sample will be used for the CF Canada funded genetic modifier study.
- 10ml (or the remainder) will be transferred to a serum tube and transferred to the laboratory for processing. Samples will be centrifuged at 3000rpm and the supernatant (serum) aliquoted to 5 separate 1.5ml
 Eppendorf tubes. Aliquots will be labelled and frozen at -80°C. These aliquots to be sent to central labs and stored for future use.
- For the year 1 blood collection, 10ml blood will be collected and processed as above, frozen at -80°C, and sent to central labs.

Nasal Lavage

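### The parent-study analysis of whether poor adherence harms outcomes compares MPR with end-of-period outcomes and gives no role to the person's own pre-ETI value, which is already collected

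*Protocol*

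**What the plan says.** The Data Analysis part of Specific Aim 7 for the parent study (Treatment Adherence) lists four research questions. The third asks whether poor adherence harms outcomes, first for ETI and then for other groups of medications. The method is: "Medium term effects will be determined by comparing overall 12 and 24-month MPRs for given medications and groups of medications", set against "specific relevant outcome measures such as CT scores, LCI, FEV1, nutritional status, antibiotic use and exacerbations at the end of 12 and 24 months", with each MPR period matched to its own end point. No model, change score or baseline covariate is named.

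The general Statistical Analysis section says: "Linear mixed models will include demographic and co-morbidity covariates to adjust for confounders". It also states that "Statistical analysis of longitudinal data requires methods that can properly account for the intra-subject correlation of response measurement", and expects "more complex analyses of derived variables such as slopes, pre/post analysis and response trajectory over time". It does not name the outcome's own baseline value as a covariate, and it does not tie any of these methods to the adherence question.

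The pre-ETI values exist. For LCI, "LCI will be performed three months prior to the baseline visit and then at baseline and at 6 monthly intervals subsequently". The schedule (Table 14) also has FEV1, height and weight at months -3 and 0, and CT at month 0 in the advanced group. Elsewhere the protocol uses these values: under Specific Aim 1 the "rate of change in % predicted FEV1 (GLI – Global Lung Initiative) will be assessed from baseline to annual subsequent follow up periods", and the primary outcome is defined as a change from baseline.

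**The concern.** A CT score, LCI or FEV1 at month 12 or 24 depends heavily on where the person started. If the starting point is not in the analysis, two things follow.

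- **Possible confounding.** If people who were sicker at entry also adhere differently, part of the MPR-outcome association is entry severity. The Background (Treatment Adherence) says "By the time patients are transitioning to adult services, adherence may have reduced by 50" per cent, and the preliminary parent-study data report that pre-treatment FEV1 and LCI differ between the 12+ and 6-11 groups. Age therefore links adherence to severity. Age counts as a demographic covariate, so the open issue is severity that differs between people of the same age.
- **Lost precision.** Between-person spread that the baseline value would explain stays in the residual, whether or not there is confounding.

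At stake is the answer to a causal question that the protocol puts directly.

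**Working it through.** The protocol gives no power, effect size or alpha for this question, so there is no stated figure to reproduce. What follows is illustrative.

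**Inputs from the protocol**
- n=201: the F/F and F/M group in the LCI power table.
- n=150: the advanced-group total in Table 6, which bounds CT.
- n=87 (FEV1) and n=49 (LCI): 12-month counts in Table 3, interim and from the 12+ phase only.

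**Assumptions**
- Two-sided 5% test, linear relation, equal SDs, Fisher z approximation.
- rho is the correlation of the pre-ETI value with the follow-up value. It is not stated, so 0.3 to 0.8 is shown.
- r_b is the correlation of MPR with pre-ETI severity. It is not stated either, so 0.1 and 0.2 are used. Both correlations should be read as what is left after age.

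**A rough guide to rho.** Treat the Table 3 6-month v 12-month p-values as paired t-tests on the raw mean differences. Then SD of difference = |difference| x sqrt(n) / t, and rho = (s1² + s2² - SDdiff²) / (2 s1 s2).
- FEV1: difference 0.38, p=0.7356, n=82, so SDdiff = 10.16 and rho = (16.032² + 16.319² - 10.16²) / (2 x 16.032 x 16.319) = 0.80.
- LCI: difference 0.29, p=0.3187, n=49, so SDdiff = 2.01 and rho = 0.88.

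Both visits are on treatment, so the correlation from pre-ETI to follow-up may be lower.

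**Precision, with no confounding.** Adjustment leaves a share 1 - rho² of the outcome variance: 0.91 at rho 0.3, 0.75 at 0.5, 0.51 at 0.7 and 0.36 at 0.8. An effect of r=0.15 on the unadjusted outcome becomes about 0.15 / sqrt(1 - rho²). Power = Φ(atanh(r) x sqrt(n-3) - 1.96), plus a negligible opposite tail. At n=201:
- Unadjusted: 0.1511 x 14.07 = 2.127, and Φ(0.167) = 57%.
- rho 0.8: r = 0.15 / 0.6 = 0.25, 0.2554 x 14.07 = 3.594, and Φ(1.634) = 95%. The simpler form 0.15 x sqrt(201) / 0.6 = 3.544 gives 94%.

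| n | Unadjusted | rho 0.3 | rho 0.5 | rho 0.7 | rho 0.8 |
|---|---|---|---|---|---|
| 201 | 57% | 61% | 69% | 85% | 94-95% |
| 150 | 45% | 49% | 56% | 73% | 87% |
| 87 | 28% | 31% | 36% | 50% | 65% |
| 49 | 18% | 19% | 22% | 30% | 41% |

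**Confounding, with no true adherence effect.** The unadjusted comparison then has correlation r_b x rho. The chance of a nominally significant result uses the same formula. For example, with r_b 0.2, rho 0.8 and n=201: r = 0.16, 0.1614 x 14.07 = 2.271, and Φ(0.311) = 62%.

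| n | r_b 0.1, rho 0.5 | r_b 0.1, rho 0.8 | r_b 0.2, rho 0.5 | r_b 0.2, rho 0.8 |
|---|---|---|---|---|
| 201 | 11% | 20% | 29% | 62% |
| 87 | 7% | 11% | 15% | 32% |

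With r_b = 0 the rate is the nominal 5%.

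**Covariate or change score.** A change score has variance 2(1 - rho) relative to the unadjusted outcome. That is 1.4 at rho 0.3, where it loses power (43% against 57% at n=201), so it helps only above rho 0.5. Covariate adjustment does not carry this penalty.

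**The case against.** The strongest reply is that the protocol is silent here and has not decided against baseline adjustment. The sentence pairs each MPR period with an assessment time and does not say whether the outcome enters as a level, a change or an adjusted value. The general section promises mixed models, pre/post analysis and confounder adjustment, and a covariate list can sit in an SAP, which was not available. This stands in part: a reader might infer that the protocol rules out the pre-ETI value, and it does not. But the sentence does fix the exposure, the outcomes and their timing at the end of the period, and the general section's covariates stop at demographics and co-morbidity. An analyst who follows that wording would compare end values.

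A reader might also infer that entry severity will be mistaken for an adherence effect. The documents do not support that as a certainty. The only link they give runs through age, which a demographic covariate would handle, and they give no correlation between MPR and severity within age.

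The illustration has limits too. The rough rho values come from two on-treatment visits with different numbers of people and an unnamed test. n=201 is generous for CT and, on the interim counts, for LCI and FEV1. Antibiotic use and exacerbations are counts over a period, not levels at a visit, and Specific Aim 6 already sets IV courses against the five years before ETI.

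Finally, for medications taken before ETI, the pre-ETI value may already reflect earlier adherence to the same drugs. Adjusting for it then answers a narrower question. That is a reason to state the estimand, not to leave the baseline value out.

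**Conclusion.** The point holds for CT score, LCI, FEV1 and nutritional status: as written, the analysis gives the collected pre-ETI value no role. Confounding by entry severity is conditional on a relation between severity and MPR beyond age, which is plausible but of unstated size and direction. The loss of precision does not need that relation. It is slight if rho is about 0.3 (57% against 61% at n=201, assumed r=0.15) and substantial at 0.7 or more (57% against 85% at 0.7 and about 94% at 0.8). Absolute power is lower at the numbers likely for CT and LCI. All of these figures rest on assumed correlations. This is a worthwhile improvement to one secondary analysis and does not affect the primary outcome.

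**What to change.** In the Data Analysis part of Specific Aim 7 (parent study), under the question on adherence and outcomes, state that:

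- CT score, LCI, FEV1 and BMI z-score at 12 and 24 months are each modelled on the MPR for that period, with the person's pre-ETI value of the same outcome, age and genotype as covariates, and that the MPR coefficient is reported;
- antibiotic use is modelled as a count over the period, with the pre-ETI IV antibiotic rate from Specific Aim 6 as a covariate;
- for medications other than ETI, the coefficient is the effect of adherence since ETI was started, because the pre-ETI value may already reflect earlier adherence.

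The cost is a few sentences of analysis text. No new data are needed. People without a pre-ETI value would rely on the multiple imputation already planned, with the complete-case analysis as the stated sensitivity check.
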